### **3.2 Exclusion Criteria**

Subjects meeting any of the criteria below may not participate in the study:

1. Received prior therapy with VEGF-TKI, immune checkpoint inhibitor, an anti-PD-1, anti-PD-L1, or anti PD L2 agent or with an agent directed to another stimulatory or co-inhibitory T-cell receptor (eg, CTLA-4, OX 40, CD137).
2. Received prior systemic anti-cancer therapy including investigational agents within 3 weeks prior to registration. **NOTE:** Participants must have recovered from all AEs due to previous therapies to  $\leq$  Grade 1 or baseline. Participants with  $\leq$  Grade 2 neuropathy may be eligible. **NOTE:** If participant received major surgery, they must have recovered adequately from the toxicity and/or complications from the intervention prior to starting study treatment.
3. Received more than two prior chemotherapy regimens for metastatic prostate cancer. Prior therapy with androgen receptor axis targeted agents is allowed but needs to be discontinued at least 2 weeks prior to study therapy. Prior therapy with Rad-223 or other radiopharmaceuticals is permitted but study therapy should be started at least 4 weeks after the last dose.
4. Concurrent treatment with anti-androgen medications. **NOTE:** LHRH agonists and GNRH antagonists may be continued. All oral anti androgens should be discontinued.
5. Received prior radiotherapy within 2 weeks of start of study treatment. Participants must have recovered from all radiation-related toxicities, not require corticosteroids, and not have had radiation pneumonitis. A 1-week washout is permitted for palliative radiation ( $\leq$  2 weeks of radiotherapy) to non-CNS disease.
6. Currently participating in or has participated in a study of an investigational agent or has used an investigational device within 3 weeks prior to the first dose of study treatment. **NOTE:** Participants who have entered the follow-up phase of an investigational study may participate as long as it has been 3 weeks after the last dose of the previous investigational agent.
7. Uncontrolled blood pressure (Systolic BP $>140$  mmHg or diastolic BP  $>90$  mmHg despite an optimized regimen of antihypertensive medication.

8. Presence of non-healing wounds after surgical procedures.
9. Known active CNS metastases and/or carcinomatous meningitis. Participants with previously treated brain metastases may participate provided they are radiologically stable, i.e. without evidence of progression for at least 4 weeks by repeat imaging (note that the repeat imaging should be performed during study screening), clinically stable and without requirement of steroid treatment for at least 14 days prior to first dose of study treatment.
10. Received a live vaccine or live-attenuated vaccine within 30 days prior to the first dose of study drug. Administration of killed viruses are allowed. All COVID-19 vaccines are permitted at any time before or during the study.
11. Significant cardiovascular impairment: history of congestive heart failure greater than New York Heart Association (NYHA) Class II, unstable angina, myocardial infarction or stroke within 6 months of the first dose of study drug, or cardiac arrhythmia requiring medical treatment at Screening.
12. Bleeding or thrombotic disorders or subjects at risk for severe hemorrhage. The degree of tumor invasion/infiltration of major blood vessels (e.g. carotid artery) should be considered because of the potential risk of severe hemorrhage associated with tumor shrinkage/necrosis following lenvatinib therapy.
13. Subjects having  $> 1+$  proteinuria on urine dipstick testing unless a 24-hour urine collection for quantitative assessment indicates that the urine protein is  $< 1$  g/24 hours.
14. Diagnosis of immunodeficiency or is receiving chronic systemic steroid therapy (in dosing exceeding 10 mg daily of prednisone equivalent) or any other form of immunosuppressive therapy within 7 days prior to the first dose of study drug.
15. Severe hypersensitivity ( $\geq$  Grade 3) to pembrolizumab and/or any of its excipients.
16. Severe hypersensitivity ( $\geq$  Grade 3) to lenvatinib and/or any of its excipients.
17. Active autoimmune disease that has required systemic treatment in the past 2 years (i.e. with use of disease modifying agents, corticosteroids or immunosuppressive drugs). Replacement therapy (eg., thyroxine, insulin, or physiologic corticosteroid replacement therapy for adrenal or pituitary insufficiency, etc.) is not considered a form of systemic treatment. Replacement steroids for adrenal insufficiency or daily dose equivalent of 10 mg prednisone are allowed.
18. History of severe (non-infectious) pneumonitis/interstitial lung disease that required steroids or has current pneumonitis/interstitial lung disease.
19. Active uncontrolled infection.

20. Known additional malignancy that is progressing or has required active treatment within the past 3 years. **NOTE:** Participants with basal cell carcinoma of the skin, squamous cell carcinoma of the skin or carcinoma in situ (e.g. breast carcinoma, cervical cancer in situ) that have undergone potentially curative therapy are not excluded. Subjects with other solid tumors treated curatively and without evidence of recurrence for at least 2 years prior to enrollment may be eligible for study after discussion with the sponsor-investigator.
21. Known history of Human Immunodeficiency Virus (HIV). **NOTE:** HIV testing is not required unless mandated by a local health authority.
22. Known history of Hepatitis B (defined as Hepatitis B surface antigen [HBsAg] reactive) or known active Hepatitis C virus (defined as HCV RNA [qualitative] is detected) infection. **NOTE:** Hepatitis B and Hepatitis C testing is not required unless clinical history indicates that this is likely.
23. Known history of active TB (Bacillus Tuberculosis).

#### **4. SUBJECT REGISTRATION**

All subjects must be registered through HCRN's electronic data capture (EDC) system. A subject is considered registered when an "On Study" date is entered into the EDC system. Subjects must be registered prior to starting protocol therapy. Protocol therapy must begin **within 5 business days** of study registration.

#### **5. TREATMENT PLAN**

Eligible patients will be treated with the combination of lenvatinib and pembrolizumab. A cycle equals 21 days and therapy will continue until radiographic progression, intolerable toxicity, or patient/physician wishes to discontinue protocol therapy. A maximum of 35 cycles may be administered. On Day 1, when both pembrolizumab and lenvatinib are administered, patients should take the lenvatinib per their normal routine.

If measurable disease is present, response will be assessed by RECIST 1.1 criteria. For bone only metastases at least 2 new areas of metastases will qualify as progression, and PSA response will be also reported per Prostate Cancer working Group 3 guidelines. Section 7 calendar outlines the schedule for assessments.

##### **5.1 Study Treatment Administration**

Drug	Dose	Route	Schedule	Cycle Length
Lenvatinib	20 mg	Orally	Day 1-21	3 weeks (21 days)
Pembrolizumab	200 mg	Intravenously (IV) over 30 minutes	Day 1	

A window of  $\pm$  3 days may be applied to all study visits to accommodate observed holidays, inclement weather, scheduling conflicts etc. Date and time of each drug administration should be clearly documented in subject's chart and electronic case report forms (eCRFs).

## **5.2 Lenvatinib**

Lenvatinib can be taken orally with or without food once daily. For subjects that cannot swallow the capsule: Use a medicine cup to measure about one tablespoon of water or apple juice and place into a small glass. Place the lenvatinib capsules into the small glass without breaking or crushing them. Leave the capsules in the liquid for at least 10 minutes. Stir the contents of the glass for at least 3 minutes. Drink the mixture. After drinking, rinse the glass with a small amount of additional water or apple juice and swallow the liquid. If a dose is missed and cannot be taken within 12 hours, then that dose should be skipped and the next dose should be taken at the usual time of administration.

Optimal medical management for nausea, vomiting, and/or diarrhea should be initiated prior to any lenvatinib therapy interruption or dose reduction; however, gastrointestinal toxicity should be actively managed in order to reduce the risk of development of renal impairment or renal failure.

**NOTE:** Diaries will be provided to subjects for completion of oral medication administration. Subjects will be asked to bring the diary and medication container to each clinic visit. Dose modification guidelines can be found in Section 6.

## **5.3 Pembrolizumab**

Pembrolizumab 200 mg will be administered as a 30 minute IV infusion every 3 weeks. Sites should make every effort to target infusion timing to be as close to 30 minutes as possible. However, given the variability of infusion pumps from site to site, a window of -5 minutes and +10 minutes is permitted (i.e., infusion time is 30 minutes: -5 min/+10 min).

## **5.4 Concomitant Medications**

### **5.4.1 Allowed Concomitant Medications**

All treatments that the investigator considers necessary for a participant's welfare may be administered at the discretion of the investigator in keeping with the community standards of medical care. Bisphosphonate therapy can be continued. All concomitant medication will be recorded on the case report form (CRF) including all prescription, over-the-counter (OTC), herbal supplements, and IV medications and fluids. If changes occur during the trial period, documentation of drug dosage, frequency, route, and date may also be included on the CRF.

All concomitant medications received within 28 days before the first dose of trial treatment and 30 days after the last dose of trial treatment should be recorded. Concomitant medications administered after 30 days after the last dose of trial treatment should be recorded if associated with SAEs and ECIs as defined in Section 11.

#### **5.4.2 Prohibited Concomitant Medications**

Participants are prohibited from receiving the following therapies during the Screening and Treatment Phase of this trial:

- Antineoplastic systemic chemotherapy or biological therapy
- Immunotherapy not specified in this protocol
- Chemotherapy not specified in this protocol
- Investigational agents other than pembrolizumab and lenvatinib
- Radiation therapy
- Live vaccines within 30 days prior to the first dose of study treatment and while participating in the study. Examples of live vaccines include, but are not limited to, the following: measles, mumps, rubella, varicella/zoster, yellow fever, rabies, BCG, and typhoid vaccine. Seasonal influenza vaccines for injection are generally killed virus vaccines and are allowed; however, intranasal influenza vaccines (eg, FluMist®) are live attenuated vaccines and are not allowed.
- Systemic glucocorticoids for any purpose other than to modulate symptoms from an event of clinical interest of suspected immunologic etiology. The use of physiologic doses of corticosteroids may be approved after consultation with the sponsor-investigator.

Participants who, in the assessment by the investigator, require the use of any of the aforementioned treatments for clinical management should be removed from the study. All treatments that the investigator considers necessary for a participant's welfare may be administered at the discretion of the investigator in keeping with the community standards of medical care.

Medications or vaccinations specifically prohibited in the exclusion criteria are not allowed during the ongoing study. If there is a clinical indication for any medication or vaccination specifically prohibited during the study, discontinuation from study therapy or vaccination may be required. The final decision on any supportive therapy or vaccination rests with the investigator and/or the participant's primary physician. However, the decision to continue the participant on study treatment requires the mutual agreement of the investigator, the sponsor-investigator and the participant. There are no prohibited therapies during the Post-Treatment Follow-up Phase.

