#### **6.4 Protocol Therapy Discontinuation**

In addition to discontinuation from therapy related to toxicities as outlined above, a subject will also be discontinued from protocol therapy and followed per protocol under the following circumstances outlined below. The reason for discontinuation of protocol therapy will be documented on the electronic case report form (eCRF)

- Completion of maximum of 35 cycles of study treatment.
- Documented disease progression per RECIST 1.1 (subjects with measurable disease) or PCWG (subjects without measurable disease). If a subject is receiving clinical benefit (as determined by treating physician), treatment can continue after discussion with sponsor-investigator.
- Site investigator determines a change of therapy would be in the best interest of the subject
- Subject requests to discontinue protocol therapy, whether due to unacceptable toxicity or for other reasons
  - In a subject decides to prematurely discontinue protocol therapy (“refuses treatment”), the subject should be asked if he or she may still be contacted for further scheduled study assessments. The outcome of that discussion should be documented in both the medical records and in the eCRF.
- If protocol therapy (both drugs) is interrupted for  $\geq 42$  days from the expected day of the next treatment. If one drug is permanently discontinued, treatment with the other drug may continue at investigator discretion.

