#### **6.6 Safety Follow Up**

The safety follow-up visit should only occur when subjects permanently stop study treatment for whatever reasons (toxicity, progression, or other reason) and should be performed 30 days (+ 7 days) after the last dose of treatment. Participants with an AE of Grade  $> 1$  will be followed until the resolution of the AE to Grade 0-1 or until the beginning of a new anti-cancer therapy, whichever occurs first. SAEs that occur within 90 days of the end of treatment or before initiation of a new anti-cancer treatment should also be followed and recorded. The Day 90 assessment may be performed via phone call, email or other avenues as appropriate.

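### Section 5.4.2 takes patients who need a prohibited therapy off the study, while Sections 6.4, 6.6 and 6.7 stop treatment and keep following them

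*Combined protocol and SAP*

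**What the plan says.** Section 5.4.2 has seven bullets of therapy prohibited during screening and treatment: systemic chemotherapy or biological therapy, other immunotherapy, other chemotherapy, other investigational agents, radiation, live vaccines, and systemic glucocorticoids with stated exceptions. Participants who, in the investigator's assessment, "require the use of any of the aforementioned treatments for clinical management should be removed from the study".

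The following paragraph of 5.4.2 is softer. Where a prohibited medication or vaccination is clinically indicated, "discontinuation from study therapy or vaccination may be required", and "the decision to continue the participant on study treatment requires the mutual agreement of the investigator, the sponsor-investigator and the participant". It closes with "There are no prohibited therapies during the Post-Treatment Follow-up Phase".

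Section 6.4 gives the general rule for stopping treatment: "a subject will also be discontinued from protocol therapy and followed per protocol under the following circumstances". One listed circumstance is "Site investigator determines a change of therapy would be in the best interest of the subject".

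Section 6.5 deals separately with a subject who chooses to leave the protocol itself and not only its therapy. There the plan speaks of removal of a subject from the study.

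Section 6.6 opens with "The safety follow-up visit should only occur when subjects permanently stop study treatment for whatever reasons" and sets that visit at 30 days after the last dose. Section 6.7 follows patients who stopped without progression every 6 months until progression, then for survival every 6 months for 5 years. The calendar's long-term follow-up column has a row for survival status and subsequent therapy.

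**The concern.** A site that needs to know what to do when a patient requires a prohibited therapy will look in 5.4.2, and the instruction there is to take the patient off the study. The rest of the plan would stop treatment, or agree to continue it, and keep the patient under observation.

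The trigger is plausible. Radiation is barred with no exception for palliative use, while exclusion criterion 5 in Section 3.2 anticipates palliative radiation in this population and the rPFS definition anticipates bone disease.

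Overall survival is the most exposed endpoint. Section 9.8.3 censors living patients when last confirmed alive, and Section 12.4.2 analyses OS by Kaplan-Meier, which assumes that censoring is unrelated to prognosis. A patient who leaves because radiation or another systemic therapy has become necessary probably has a worse outlook than one who stays. Ending contact at that point would tend to make the survival curve look better than it is. If sites read the sentence differently, comparable patients would also be followed differently.

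**Working it through.** No arithmetic on an endpoint applies, because the documents do not say how often a prohibited therapy is expected to be needed. The check compares the sections.

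**1. Does leaving the study mean the same as leaving treatment in this protocol?** Section 6.4 covers stopping protocol therapy with follow-up kept. Section 6.5 covers leaving the protocol, contrasts that with leaving therapy alone, requires a complete final evaluation, and uses the language of removal from the study. The wording in 5.4.2 matches 6.5, so the literal reading is that follow-up ends.

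**2. Does 6.4 override 5.4.2?** Section 6.4 has five main circumstances: 35 cycles completed, progression, best interest, subject request, and interruption of 42 days or more. None of the five names a prohibited therapy. The best-interest item can cover a needed change of treatment, but a reader must infer that against an explicit instruction in 5.4.2.

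**3. Does the next paragraph of 5.4.2 settle it?** Only in part. It makes stopping treatment possible but not mandatory, allows continuation by agreement, and presupposes a follow-up phase after treatment. That is inconsistent with removal. However, it opens with items prohibited by the exclusion criteria and refers to medication or vaccination, so it does not clearly reach radiation.

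**4. What would a removed patient lose?**

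| Planned follow-up | Source | Lost under a literal reading? |
|---|---|---|
| Safety visit 30 days after last dose | 6.6 | Yes |
| SAE reporting to 90 days | 11.2.2.1 | Only if no new anti-cancer treatment starts, since that closes the window anyway |
| Contact every 6 months until progression | 6.7 | Yes, if removed before progression |
| Survival contact every 6 months for 5 years after progression | 6.7 | Yes: up to 60/6 = 10 contacts |
| Imaging after treatment stops | 6.7; Section 7 footnote 5 | Little: it is discretionary, and eCRF tumor follow-up ends when another treatment starts |

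The safety loss therefore falls mainly on patients removed for reasons other than cancer treatment, such as steroids or a live vaccine. The protocol does not say whether palliative radiation counts as new anti-cancer treatment for the SAE window. The survival loss applies whatever the trigger.

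**The case against.** The best defence is that the plan, read as a whole, shows that follow-up is meant to continue. Footnote 4 to the calendar speaks of subjects coming off study without progression and still has their PSA obtained at the investigator's discretion, so the plan elsewhere uses off-study language for patients it keeps observing. The calendar row for survival and subsequent therapy presupposes that patients who move to other treatment remain in follow-up. Section 6.6 applies whatever the reason for stopping. Section 6.5, even for a true exit, asks for all efforts to complete assessments. For a patient still in screening, removal is also the natural outcome.

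This stands as evidence of intent, and it makes the harm smaller and hypothetical. It does not remove the conflicting instruction for patients on treatment.

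Three stronger readings are tempting but not supported:

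- A reader might infer that "All treatments that the investigator considers necessary for a participant's welfare may be administered at the discretion of the investigator" contradicts removal. It does not. It says that care will not be withheld and is silent on whether the patient stays on study.
- A reader might infer that steroids for immune-related events trigger removal, because the exemption uses the term event of clinical interest and the list in 11.1.7 does not name those events. That list is not worded as exhaustive, and Section 5.5, Table 1 and the severity rule in the overlapping-toxicities section show that such steroid use is intended.
- A reader might infer a loss of power for 6-month rPFS. Any such figure would need an assumed removal rate and an assumed handling of removed patients. The documents supply neither, and imaging after treatment stops is discretionary in any case.

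**Conclusion.** The inconsistency is real and the point is minor. The removal sentence in 5.4.2, taken literally, ends follow-up that 6.4, 6.6, 6.7 and the calendar plan to continue. The consequence is conditional: it requires a site to apply the sentence as written, and the bias in OS further requires that needing the therapy is related to prognosis, which is probable but is a judgment and not a figure in the plan. OS is a secondary endpoint, estimated without a hypothesis test, in at most 50 enrolled patients. No numerical effect on any endpoint can be derived, and many sites would probably keep following their patients. Confidence is high that the texts conflict, and much lower that practice would be affected.

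**What to change.** In Section 5.4.2, replace *removed from the study* with: *discontinued from protocol therapy per Section 6.4, unless continuation is agreed as described below, and followed per Sections 6.6 and 6.7*. The middle clause points to the existing mutual-agreement rule and does not widen it. No other wording in 5.4.2 needs to change for this point.

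The cost is one phrase in a wording amendment. It adds no patients, visits or procedures beyond the follow-up already planned, and the sample size, endpoints and analyses are unchanged. It is best made early, since contact lost after a patient has been removed may not be recoverable.

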#### **5.5 Supportive Care**

Participants should receive appropriate supportive care measures as deemed necessary by the treating investigator. Suggested supportive care measures for the management of AEs with potential immunologic etiology are outlined along with the dose modification guidelines. Where appropriate, these guidelines include the use of oral or IV treatment with corticosteroids, as well as additional anti-inflammatory agents if symptoms do not improve with administration of corticosteroids. Note that several courses of steroid tapering may be necessary as symptoms may worsen when the steroid dose is decreased. For each disorder, attempts should be made to rule out other causes such as metastatic disease or bacterial or viral infection, which might require additional supportive care. The treatment guidelines are intended to be applied when the Investigator determines the events to be related to pembrolizumab.

**NOTE:** If after the evaluation of the event, it is determined not to be related to pembrolizumab, the Investigator does not need to follow the treatment guidance. Refer to guidelines regarding dose modification and supportive care.

It may be necessary to perform conditional procedures such as bronchoscopy, endoscopy, or skin photography as part of evaluation of the event.

